10.3.2 Safety Analyses

All safety analyses will be performed on the Treated population.

Endpoint	Statistical Analysis Methods

Incidence of DLTs, AEs, SAEs, AEs leading to discontinuation, deaths
 
AEs will be graded according to CTCAE (version 4.0).
	
DLT rate by dose level; Frequency distribution of treated participants with AE using the worst CTC grade.
 
Participants will only be counted (1) once at the preferred term (PT) level, (2) once at the system organ class (SOC) level, and (3) once in the 'Total participant' row at their worst CTC grade, regardless of SOC or PT.
 
Deaths will be summarized using frequency distribution

Laboratory abnormalities
 
Laboratory values will be graded according to CTCAE (version 4.0)
	
Laboratory abnormalities will be summarized.
 
Lab shift table using the worst CTC grade on treatment per participant.

10.3.6 *Outcomes Research Analyses*

10.3.6.3 *Other Analyses*

Not Applicable

10.3.7 *Interim Analyses*

Data were reviewed during the dose escalation/de-escalation evaluation phase (Part 1 and Part 1A) to determine the proposed combination regimens for Part 2 and Part 1B. Comprehensive analyses for Part 1 including safety, [REDACTED], and preliminary efficacy data were conducted to support dose selection for Part 2 (RP2D) as appropriate.

An interim analysis (IA) of Part 2 and Part1B cohorts will be conducted after an overall total of approximately 100 treated participants (including approximately 60 treated participants from Part 2) have a minimum of 4 months of follow-up after the first treatment (corresponding to at least 2 tumor assessments). The objectives of this IA will be a review of the safety data and to provide preliminary efficacy.

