4 OBJECTIVES AND ENDPOINTS

Table 4-1: Objectives and Endpoints: Parts 1 and 1A

Objectives	Endpoints
Primary	

To characterize the safety and tolerability of combination therapiesTo establish recommended dosing regimen for the combination (nivolumab plus ipilimumab plus trametinib OR nivolumab plus trametinib)	
DLTs in Part 1 and Part 1A, only, observed for 1 treatment cycle (4 weeks for the doublet regimen and 8 weeks for the triplet regimen)Safety (including but not limited to): AEs, SAEs, deaths, and clinical laboratory abnormalities per CTCAE (version 4.0)
Secondary	

To evaluate preliminary efficacy	
ORR DCR, DOR, TTR, and PFS by investigator per RECIST v1.1OS

AE, adverse event; CTCAE, Common Terminology Criteria for Adverse Events; DCR, disease control rate; DLTs, dose limiting toxicities; DOR, duration of response; [REDACTED]; ORR, objective response rate; OS, overall survival; PFS, progression free survival; [REDACTED]; RECIST, Response Evaluation Criteria in Solid Tumors; SAE, serious adverse event; TTR, time to response.

Table 4-2: Objectives and Endpoints: Parts 1B and 2

Objectives	Endpoints
Primary 
To evaluate the ORR in all participants treated with nivolumab plus ipilimumab and trametinib in the 2L and 3L+^a setting (Parts 1B and 2, respectively) and regorafenib in 3L+^a (Part 2 only)	
ORR by investigator^b
Secondary 
To evaluate efficacy in all participants treated with nivolumab plus ipilimumab and trametinib in the 2L and 3L+^a setting (Parts 1B and 2, respectively); and regorafenib in 3L+^a (Part 2 only) [REDACTED] [REDACTED]	
BOR, DCR, DOR, TTR, and PFS by investigator^bOS

To characterize the safety and tolerability of combination therapies	
Safety (including but not limited to): AEs, SAEs, deaths, and clinical laboratory abnormalities per CTCAE (version 4.0)

Table 4-2: Objectives and Endpoints: Parts 1B and 2

Objectives	Endpoints

AE, adverse event; [REDACTED], BOR, best overall response; [REDACTED]; CTCAE, Common Terminology Criteria for Adverse Events; DCR, disease control rate;; DOR, duration of response; [REDACTED]

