Interim analysis will be performed to evaluate preliminary safety and efficacy per **Section 10.3.7**.

The study design schematic is presented in [Figure 5.1-1](#).

Figure 5.1-1: Study Design Schematic

Ipi, ipilimumab; mCRC, metastatic colorectal cancer; MSS, microsatellite stable; Nivo, nivolumab; pMMR, proficient mismatch repair, QD, quaque die, once daily; Q4W, every 4 weeks; Q8W, every 8 weeks; wk, week; 2L, second line; 3L, third line; 3L+, third line plus.

^a See [Table 7.2-1](#) for unique cohort numbers for dose escalation and de-escalation.

^b Participants in Part 1A were assigned to each treatment cohort on an alternating basis in IRT (interactive response technology). NOTE: Enrollment is closed in Part 1 and Part 1A cohorts.

NOTE: Participants in each part of the study will be treated until progression, unacceptable toxicity, withdrawal of consent, or a maximum of 2 years. Maximum treatment duration is not applicable to standard of care therapy (regorafenib).

5.1.1 **Part 1 and Part 1A: Dose Optimization**

The dose optimization phase of the study has completed. Enrollment is closed in all Part 1 and Part 1A cohorts. There will be ongoing safety data review, but no further DLT evaluations.

The DLT observation period will be one cycle for both treatment regimens, i.e., 4 weeks for the doublet regimen (Part 1); 8 weeks for the triplet regimen (Part 1A).

Following 3+3 design in Part 1 (doublet regimen) and Part 1A (triplet regimen), trametinib dosing regimen could be either escalated or de-escalated for the next treatment cohort based on the number of DLT's observed from previous cohort. Table 5.1.1-1 describes dose escalation or de-escalation plan for trametinib as a general rule. However, the totality of the safety data observed, not only the adverse events that meet the DLT definition, will be considered when making decisions for dose escalation or de-escalation. Such decisions will be made and documented in conjunction with treating physicians and collaborator at the end of the DLT observation period.

Table 5.1.1-1: Dose Escalation and De-Escalation Plan Per 3+3 Design

Number of Participants with DLT at a Given Dose Level	Escalation And De-Escalation Plan
0 out of 3, or < 2 out of 6	May Enter 3 additional patients at the next higher dose level.
1 out of 3	Enter 3 additional patients at the same dose level.
2-3 out of 3, or ≥ 2 out of 6	Enter 3 additional patients at the next lower dose level

Part 1 Doublet Regimen, Cohort 1 Group

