All participants will start at the same trametinib dose level and frequency (daily in continuous regimen vs. intermittent regimen) within a particular cohort throughout the first cycle (doublet and triplet regimens). No dose escalation or de-escalation within a particular cohort is permitted once study treatment starts during the first cycle (doublet and triplet regimens) for DLT observation. If participants don't tolerate the study treatment at the pre-specified starting dose during the first cycle/DLT observation period, study treatment must be permanently discontinued*. After the DLT observation period, the daily dose of trametinib may be modified to manage participants' adverse events (see [Section 7.4.4](#)). Modification of trametinib dosing frequency is not permitted throughout treatment duration, except dosing delay per dose modification guidelines ([Appendix 6](#)).

Toxicities will be considered DLTs only if they occur in Cycle 1 for the doublet and triplet regimens. Participants are required to complete Cycle 1 ($\geq 50\%$ of the planned cumulative dose) to be considered evaluable unless discontinuation occurred due to a DLT.

DLTs are specified in [Section 5.1.1.1](#) below.

*Under rare circumstances, participants may resume study treatment at a lower dose level for trametinib if deemed medically appropriate by investigators. BMS Medical Monitor or designee

should be consulted before resuming study treatment. Dose modification should be approved by BMS on a case by case basis (refer to [Sections 7.4](#) and [8](#)). Participants will be analyzed based on initial cohort assignment regardless of dose modification received.

Part 1B and Part 2: ENROLLMENT CLOSED

Per Revised Protocol 02, Part 2 (████████ phase for triplet regimen including SOC arm) and Part 1B (████████ for triplet regimen) will be initiated based on the totality of safety data observed from this study and relevant ongoing clinical studies. The observed benefit/risk profile from Part 1 and 1A has determined a recommended Phase 2 dose to be the triplet regimen of nivolumab 6 mg/kg Q4W + ipilimumab 1 mg/kg Q8W + trametinib 1.5 mg continuous QD. There will be ongoing safety data review, but no further DLT evaluations.

5.1.1.1 *Dose Limiting Toxicity*

As Part 1 and Part 1A are completed, there will be ongoing safety data review, but no further DLT evaluations.

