For the purpose of guiding dose regimen, DLTs will be defined based on the incidence, duration and grade of AEs for which no alternate cause can be identified. Adverse events will be evaluated according to the NCI CTCAE (version 4.0). DLT(s) during the first cycle of treatment (the DLT evaluation period) will be observed for the first 4 weeks for the doublet regimen and first 8 weeks for the triplet regimen. Every attempt must be made to assign relationship to the individual study treatment, if possible, or to the combination regimen, nivolumab/ipilimumab/trametinib combination or nivolumab/trametinib combination. To meet criteria for dose limiting toxicity, adverse events have to be at least possibly related to study treatment, and not to disease progression, be clinically relevant and a clinically relevant shift from baseline.

Participants who withdraw from the study during the DLT evaluation interval for reasons other than a DLT may be replaced at the same dose of the study treatment.

Dose limiting toxicities can include the following adverse events (meeting the preceding criteria):

1) Hepatic DLT

- a) Any of the following events will be considered a hepatic DLT (Note that this special category of DLT uses ULN rather than Common Toxicity Criteria Grade for definition.):
 - i) For participants with normal baseline AST and ALT values: AST or ALT $> 8 \times$ ULN
 - ii) For participants with normal baseline Total bilirubin (TBIL) value: TBIL $> 5 \times$ ULN
 - iii) For participants with normal baseline AST and ALT and normal baseline bilirubin values: AST or ALT $> 3 \times$ ULN and concurrent total bilirubin $> 2 \times$ ULN without initial findings of cholestasis (elevated serum alkaline phosphatase $\geq 2 \times$ ULN) or other reasons to explain the combination of increased aminotransferases and TBIL
 - iv) For participants with abnormal baseline AST or ALT or abnormal baseline bilirubin values: [AST or ALT $> 2 \times$ baseline AND $> 8 \times$ ULN], combined with [TBIL $> 2 \times$ baseline AND $> 2 \times$ ULN] without initial findings of cholestasis (elevated serum alkaline phosphatase $\geq 2 \times$ ULN) or other reasons to explain the combination of increased aminotransferases and TB,

2) Nonhepatic Nonhematologic DLT

- a) Any of the following events will be considered a nonhepatic nonhematologic DLT:

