- e) Grade \geq 3 hemolysis (ie, requiring transfusion or medical intervention such as steroids) or any clinically relevant hemolysis as follows:
 - i) Any clinically meaningful laboratory evidence of hemolysis and Grade 2 creatinine elevation
 - ii) Any clinically meaningful laboratory evidence of hemolysis and Grade 3 thrombocytopenia
 - iii) Any clinically meaningful laboratory evidence of hemolysis with more than a 3gm/dL drop in hemoglobin (or CTCAE hemoglobin level \geq Grade 3).

5) Any toxicity requiring dose delay of study treatment during cycle 1 resulting in:

- a) Delay of $>$ 4 weeks in initiating Cycle 2
- b) Participant receives less than 50% of intended total dose of any study drug treatment
- c) Participant only receives one dose of nivolumab in the triplet regimen

5.1.1.2 *Toxicity Management during DLT Observation*

Optimal medical management must be implemented for all participants in this study, including the DLT observation phase in Part 1 and Part 1A. As Part 1 and Part 1A are completed, there will be ongoing safety data review, but no further DLT evaluations.

Adequate patient education and frequent follow-up with participants by investigator site staff must be performed to manage treatment emergent toxicities. Refer to [Section 3.3.2](#) for AE management guidelines. Prophylaxis/prevention measures relating to trametinib related skin toxicities and diarrhea are described below and in [Appendix 6](#):

- Rash: Rash prophylaxis/prevention is recommended for the first 6 weeks of study treatment with trametinib. Participants who develop rash/skin toxicities should be seen by a qualified physician and should receive evaluation for symptomatic/supportive care management.
- Diarrhea: Loperamide or other anti-diarrheal treatment should be accessible prior to start of study treatment with trametinib so loperamide or other anti-diarrheal administration can begin at the first signs of diarrhea, if clinically indicated.

5.1.2 *Part 1B: [REDACTED] The Triplet Regimen*

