10.2 Populations for Analyses

For purposes of analysis, the following populations are defined below. The population definition will apply to all cohorts unless specified otherwise:

Population	Description
Enrolled	All participants who sign informed consent and were registered into IRT.
Randomized	All participants who are randomized to any treatment in Part 2 (primary efficacy analysis population for Part 2 and outcome research assessment analysis population for Part 2).
Treated	All participants who take at least 1 dose of study medication.
Response-evaluable	All treated (randomized for Part 2) participants with measurable disease at baseline and at least one post-baseline tumor assessment.

Population	Description

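### Section 10.3.2 puts the DLT rate by dose level on the Treated population without exception, which does not agree with the DLT-evaluable rule in Section 5.1.1 (minor, reporting only)

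*Combined protocol and SAP*

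**What the plan says.** Section 10.3.2 opens with a general rule: "All safety analyses will be performed on the Treated population". The first row of its table puts DLTs together with adverse events and deaths, and gives the method as "DLT rate by dose level; Frequency distribution of treated participants with AE using the worst CTC grade". No exception is made for DLTs. Section 10.2 defines Treated as "All participants who take at least 1 dose of study medication".

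The dose-finding sections define the DLT count differently:

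- Section 5.1.1 requires completion of Cycle 1, meaning at least 50% of the planned cumulative dose, "to be considered evaluable unless discontinuation occurred due to a DLT".
- Section 5.1.1.1 adds: "Participants who withdraw from the study during the DLT evaluation interval for reasons other than a DLT may be replaced at the same dose".
- Table 5.1.1-1 decides on the "Number of Participants with DLT at a Given Dose Level", with thresholds expressed out of 3 or out of 6.

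Table 4-1 lists two primary endpoints for Parts 1 and 1A. One is "DLTs in Part 1 and Part 1A, only, observed for 1 treatment cycle"; the other is general safety.

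**The concern.** The two rules give different denominators whenever someone is treated but not evaluable. The replacement provision shows that the protocol foresees this. A participant who takes one dose and leaves for an unrelated reason was not observed for the 4- or 8-week DLT window, yet on the Treated population that participant counts as a complete non-event.

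The usual direction is towards a lower rate. Item 5(b) of Section 5.1.1.1 already makes it a DLT when a toxicity-driven delay in Cycle 1 means that "Participant receives less than 50% of intended total dose of any study drug treatment". Participants left out of the evaluable set will therefore mostly have fallen short for reasons other than toxicity, and will usually have no DLT.

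At stake is whether a reader can reconcile a reported primary endpoint with the decision rule it belongs to, and whether the reported rate looks somewhat more favourable than the one the 3+3 rule defines.

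**Working it through.** **The plan's own figure.** The only calculated figure for the dose-finding parts is in Sections 10.1.1 and 10.1.3: about 82% probability of seeing at least one event among 6 participants at 25% incidence. Check: 1 − 0.75^6 = 0.822. It reproduces. It does not settle which participants form the DLT denominator.

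**Inputs.** Let n be the number evaluable at a level (3 or 6, Table 5.1.1-1), d the DLTs among them, and k the treated-but-not-evaluable participants without a DLT. The documents give neither d nor k for any level. I assume k = 0, 1 or 2.

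**Formulas.** Evaluable rate = d/n. Treated rate = d/(n + k). Intervals are exact (Clopper-Pearson) 95%.

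| DLTs/evaluable | k = 0 | k = 1 | k = 2 | Fall in points, k = 1 and k = 2 |
|---|---|---|---|---|
| 1/6 | 16.7% (0.4–64.1) | 1/7 = 14.3% (0.4–57.9) | 1/8 = 12.5% (0.3–52.7) | 2.4 and 4.2 |
| 2/6 | 33.3% (4.3–77.7) | 2/7 = 28.6% (3.7–71.0) | 2/8 = 25.0% (3.2–65.1) | 4.8 and 8.3 |
| 2/3 | 66.7% (9.4–99.2) | 2/4 = 50.0% (6.8–93.2) | 2/5 = 40.0% (5.3–85.3) | 16.7 and 26.7 |

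A result of 1/3 is left out because Table 5.1.1-1 then enters three more participants at the same level, so it is an interim state and not a normal final result. The 2/6 row is the de-escalation boundary.

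**Conditions for a difference.**

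- If k = 0, the two rates are identical.
- If d = 0, both rates are 0% whatever k is. Only the denominator and the interval move. For example, the upper limit 1 − 0.025^(1/n) is 45.9% for 0/6 and 41.0% for 0/7.
- If d ≥ 1 and k ≥ 1 at the same level, the Treated rate is lower.
- If a non-evaluable participant did have a Cycle 1 DLT, for example one who stopped early for another reason, the Treated rate becomes (d + 1)/(n + 1), which is higher than d/n whenever d is less than n. This is less likely given item 5(b) and the exception for DLT discontinuations, but it is why those participants should be listed.

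**The case against.** **Unseen text.** The Section 10.2 table repeats its header with no rows beneath it, so a population may have been redacted. Section 10.3 calls itself a summary and leaves participant selection to a SAP that is not included. Either could define a DLT-evaluable set. This stands, and for that reason the point cannot be that the plan lacks such a set. It does not remove the unqualified wording of Section 10.3.2, which would still have to be reconciled with any such definition.

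**A softer reading.** In the table cell, treated participants are mentioned in the adverse-event clause, and the DLT clause names no denominator. Section 10.2 also builds its response-evaluable set by adding conditions to the treated set. One could therefore apply Section 5.1.1 inside the Treated frame. That reading is available, but the opening sentence covers all safety analyses, and the neighbouring Section 10.3.1 states its Part 2 exception explicitly. An exception for DLTs should be written in the same way.

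**Perhaps nobody was non-evaluable.** The planned maxima in Sections 10.1.1 and 10.1.3 (18 in Part 1, 12 per Part 1A cohort) equal 3 × 6 and 2 × 6. They contain no visible allowance for replacements. The totals are approximate, so this does not prove k = 0, but zero is a reasonable base case.

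**Size.** Every shift in the table is small against the exact intervals. This stands, and it limits the point to traceability.

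**A tempting stronger reading.** A reader might infer that diluted DLT rates led to the wrong recommended dose. The documents do not support that. Section 5.1.1 bases decisions on the Table 5.1.1-1 counts together with the totality of the safety data, not on the Section 10.3.2 summary. Nor can one infer that dilution occurred, since no counts are given, or that the evaluable rule was in fact applied, since the documents state the rule without showing its use.

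**Conclusion.** The inconsistency is real, minor, and confined to reporting. Taken literally, Section 10.3.2 gives a primary endpoint of Parts 1 and 1A a denominator that does not agree with Section 5.1.1, the replacement rule in Section 5.1.1.1, or Table 5.1.1-1. The reported rate is lowered only at a level that has both at least one DLT and at least one treated-but-not-evaluable participant without a DLT. Under the assumption of one or two such participants, the fall is 2.4 to 8.3 points for the six-participant examples and 16.7 to 26.7 points for 2/3. Parts 1 and 1A are complete with no further DLT evaluation, and the regimen for Parts 1B and 2 is already chosen. The DLT rate nevertheless remains a listed analysis, so the text is worth correcting. Confidence is medium because a redacted row or the SAP may already define the set.

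**What to change.** In Section 10.3.2, and in the SAP, state that the DLT rate by dose level is calculated in the DLT-evaluable set as Section 5.1.1 already defines it, with no change to that definition. If a redacted row or the SAP already names such a set, refer to it. Add a listing by dose level of participants who were treated but not evaluable, giving the reason and any Cycle 1 DLT, so that no event is hidden by the exclusion. The Treated-based rate can be shown as supplementary. Keep Treated for every other safety analysis.

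The cost is one sentence and a short listing. The reported DLT rate may come out slightly less favourable.
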